Note: Blood samples may not be collected from the same arm used for VFI administration. In the event that vascular access cannot be established in both arms, a single arm may be used with documentation in the subject's records. PK/PD blood samples will be collected as close to the nominal time point as possible. Allowable windows for PK/PD blood sample collection relative to dosing will be as follows: within 30 minutes predose, \pm 1 minute through 170 minutes postdose, \pm 2 minutes through 480 minutes postdose, \pm 10 minutes through 24 hours postdose, and

± 1 day through Day 22. In the event samples for VFI and Iohexol are scheduled to be taken at the same time, VFI samples should be taken first, followed by Iohexol samples.

Table 1.6 Pharmacokinetic and Pharmacodynamic Sampling Schedule – Cohort 3 and 4 (Single-dose Administration of VFI)

Study Day	Time (Relative to Start of VFI Bolus Injection)	FD001 and FD003 PK/PD Plasma Sample	FD001 PK Urine Sample	Time (Relative to Start of Iohexol Bolus Injection)	Iohexol PD Plasma Sample
1	Predose	X	X ^a	Predose	X
	0 minutes			VFI Administration	
	15 minutes	X	0 to 2 hours ^b	-	-
	30 minutes	X		-	-
	60 minutes	X		-	-
	120 minutes	X		-	-
	160 minutes			Iohexol Administration	
	170 minutes	X	2 to 12 hours ^b	10 minutes	X
	280 minutes	-		120 minutes	X
	310 minutes	X		150 minutes	X
	340 minutes	-		180 minutes	X
	370 minutes	X		210 minutes	X
	480 minutes	X		320 minutes	X
	12 hours	X		560 minutes	X
	24 hours	X		-	-
	32 hours	X		-	-
4	72 hours	X		-	-
8	168 hours	X		-	-
15	336 hours	X		-	-
21	480 hours	X		-	-

Abbreviations: PD = pharmacodynamic; PK = pharmacokinetic; VFI = visible fluorescent injectate

a. Patients will be asked to void their bladder prior to VFI dosing; a small sample (~10mL) will be saved.

b. Urine will be collected from time 0 through 2 hours and pooled and from 2 hours through 12 hours and pooled.

A total volume of urine in each pool will be measured. Patients will be asked to void their bladder at the 2-hour and the 12-hour time point. Time of void should be recorded.

Note: Blood samples may not be collected from the same arm used for VFI administration. In the event that vascular access cannot be established in both arms, a single arm may be used with documentation in the patient records. PK/PD blood samples will be collected as close to the nominal time point as possible. Allowable windows for PK/PD blood sample collection relative to dosing will be as follows: within 30 minutes predose, ± 1 minute through 170 minutes postdose, ± 2 minutes through 480 minutes postdose, ± 10 minutes through 24 hours postdose, ± 1 hour through 32 hours postdose and ± 1 day through Day 21. In the event samples for VFI and Iohexol are scheduled to be taken at the same time, VFI samples should be taken first, followed by Iohexol samples.

6.1.3 Randomization and Treatment Assignments

This is an open-label study. Eligible subjects/patients will be enrolled in a cohort based on renal function and will be assigned sequential subject numbers.

6.1.4 Study Drug Administration

Each subject will receive at least a single dose of the VFI, which will be administered IV through a bolus injection. Subjects in Cohort 1 will receive an infusion of 5% albumin (up to a maximum volume of 7 mL/kg over 30 minutes) 130 minutes after the dose of VFI in order to measure the increase in the subject's plasma volume using the FAST PV Technology.

An IV catheter will be inserted into the subject's arm. A single dose of VFI 47 mg/3 mL will be administered as a bolus injection through the catheter. A single dose of Iohexol 5 mL will be administered as a bolus injection through the same catheter 160 minutes after administration of VFI in Cohorts 2 through 4. Subjects in Cohort 2 will receive a second dose of VFI 47 mg/3 mL bolus injection 24 hours after the initial dose of VFI in order to assess the repeatability of the FAST mGFR Technology.

For safety reasons, the first 2 subjects in Cohort 2 will receive their second dose of VFI at least 24 hours before VFI dosing in the remaining subjects. Administration of VFI will be performed in a sequential manner with at least 60 minutes between each subject.

A low-protein snack will be served prior to administration of the VFI (eg, toast, bagel or primarily carbohydrate based small portion). Water will be allowed as desired.

Standard meals will be served for Cohorts 1 and 2. Meals appropriate for the patient's medical condition will be served for Cohorts 3 and 4.

The VFI is packaged in a 10-mL, 20-mm clear glass vial with a 20-mm gray stopper and blue cap, and the product is a deeply colored lyophilized cake.

Iohexol is packaged in a clear 10 mL bottle with a brown cap, and the product is a colorless to pale-yellow liquid. Each mL of Iohexol solution contains 1.21 mg tromethamine and 0.1 mg edetate calcium disodium.

6.1.5 Concomitant Medications

For subjects in Cohorts 1 and 2, no concomitant medications (prescription, OTC, and herbal) may be administered, other than hormonal birth control, during the study unless they are prescribed by the investigator for treatment of specific clinical events (ie, AEs). However, for patients in Cohorts 3 and 4, maintenance medications as prescribed by their physicians are permitted. All medications (prescription and OTC), vitamin and mineral supplements, and herbs taken during the study will be documented on the concomitant medication electronic case report

form (eCRF). Information recorded will include: start and stop dates and times, dose and route of administration, and indication. Medications taken for a procedure should also be included.

6.1.6 Compliance

Investigational product will be administered by qualified healthcare professionals at the CRU as designated by the investigator. Details regarding dosing, including the dose administered and the date and time of dosing, will be recorded. The prepared syringes to be used for VFI and Iohexol injections will be weighed and documented before and after dosing in order to calculate the exact amount of product administered.

6.1.7 Pharmacokinetic Sampling Schedule

Pharmacokinetic samples to be taken for FD001 and FD003 at time points presented in [Table 1.4](#) (Cohort 1), [Table 1.5](#) (Cohort 2) and [Table 1.6](#) (Cohorts 3 and 4).

6.2 Evaluation of Treatment Safety

6.2.1 Adverse Events

An AE is defined as any untoward medical occurrence in a subject administered a pharmaceutical product during the course of a clinical investigation. An AE can therefore be any unfavorable and unintended sign, symptom, or disease temporally associated with the use of an investigational product, whether or not thought to be related to the investigational product.

Subjects will be monitored throughout the study for AEs, from administration of the first dose of study drug through the EOS visit. Adverse events that are identified at the last assessment visit (or the early termination visit) as specified in the protocol must be recorded on the AE eCRF with the status of the AE noted. All events that are ongoing at this time will be recorded as ongoing on the eCRF. All (both serious and nonserious) AEs must be followed until they are resolved or stabilized, or until attempts to determine resolution of the event are exhausted. The investigator should use his/her discretion in ordering additional tests as necessary to monitor the resolution of such events.

The investigator is responsible for determining whether an AE meets the definition of a SAE. A SAE is any AE occurring from ICF signing through the EOS visit that result in any of the following outcomes:

- Death
- A life-threatening adverse drug experience
- Inpatient hospitalization or prolongation of existing hospitalization
- A persistent or significant disability/incapacity
- A congenital anomaly/birth defect

Important medical events that may not result in death, be life-threatening, or require hospitalization may be considered a SAE when, based upon appropriate medical judgment, they may jeopardize the subject and may require medical or surgical intervention to prevent any of the outcomes listed in this definition. Examples of such medical events include allergic bronchospasm requiring intensive treatment in an emergency room or at home, blood dyscrasias or convulsions that do not result in inpatient hospitalization, or the development of drug dependency or drug abuse.

Significant AEs are defined as marked hematological and other laboratory abnormalities (other than those meeting the definition of serious) and any events that led to an intervention, including withdrawal of study drug, dose reduction, or significant additional concomitant therapy, other than those reported as SAEs.

6.2.2 Clinical Laboratory Assessments

Samples for laboratory assessments will be collected at time points presented in [Table 1.1](#) (Cohort 1), [Table 1.2](#) (Cohort 2), and [Table 1.3](#) (Cohorts 3 and 4). The safety laboratory parameters to be assessed are presented in below [Table 2](#).

Table 2 Clinical Laboratory Tests

Hematology	Coagulation	Serum Chemistry	Urinalysis ^{a,b,e}
Hematocrit	INR ^c	Sodium	Nitrites
Hemoglobin		Potassium	Leukocytes
Red blood cell count		Chloride	Protein
Mean corpuscular volume		Albumin	Glucose
White blood cell count		Aspartate aminotransferase	Ketones
Platelet count (estimate not acceptable)		Alanine aminotransferase	Urobilinogen
Neutrophils (absolute)		Alkaline phosphatase	Bilirubin
Eosinophils (absolute)		Creatine phosphokinase	Blood
Basophils (absolute)		Glucose ^d	pH
Lymphocytes (absolute)		Total cholesterol ^d	Specific gravity
Monocytes (absolute)		BUN	
		Creatinine	
		Total bilirubin	
		Calcium	
		Total protein	
		Phosphorous	

- a. In case of clinically significant findings, a microscopic analysis will be performed.
- b. If 1+ or greater protein is noted in the urinalysis, a calculated urine protein to creatinine ratio will be performed.
- c. Cohorts 3 and 4 only.
- d. Should be collected after fasting for a minimum of 8 hours.
- e. A urine protein to creatinine ratio will be performed only at predose on testing day and 24 hours postdose. Subjects will be fasting prior to this measurement.

6.2.3 Vital Signs

Vital signs assessments will be collected at time points presented in [Table 1.1](#) (Cohort 1), [Table 1.2](#) (Cohort 2), and [Table 1.3](#) (Cohorts 3 and 4).

Vital signs assessments will include oral temperature (°C), respiratory rate (breaths per minute), systolic and diastolic BP (mmHg) and pulse rate (bpm). Blood pressure and pulse rate will be measured after the subject has been resting quietly in a supine position or in the most recumbent position possible for at least 5 minutes.

Vital signs abnormalities that (1) are considered clinically significant initially and on confirmation, (2) require a subject to be discontinued from the study, (3) require a subject to receive treatment, or (4) require a change or discontinuation from the study drug (if applicable) will be recorded as AEs.

6.2.4 Pulse Oximetry

Oxygen saturation will be measured by pulse oximetry at time points presented in [Table 1.1](#) (Cohort 1), [Table 1.2](#) (Cohort 2), and [Table 1.3](#) (Cohorts 3 and 4).

Oxygen saturation abnormalities that (1) are considered clinically significant initially and on confirmation, (2) require a subject to be discontinued from the study, (3) require a subject to receive treatment, or (4) require a change or discontinuation from the study drug (if applicable) will be recorded as AEs.

6.2.5 Physical Examinations

Complete physical examinations (including eyes, ears, nose and throat, cardiac, peripheral vascular, pulmonary, musculoskeletal, neurologic, abdominal, lymphatic, and dermatologic systems) will be performed at time points presented in [Table 1.1](#) (Cohort 1), [Table 1.2](#) (Cohort 2), and [Table 1.3](#) (Cohorts 3 and 4) in the protocol, and abnormal findings will be carefully documented in the subject's eCRF.

An abnormal physical examination finding that is considered clinically significant and (1) requires the subject to be discontinued from the study, (2) requires the subject to receive treatment, or (3) requires a change or discontinuation of the study drug (if applicable) will be recorded as an AE.

6.2.6 Electrocardiograms

Electrocardiograms will be collected at time points presented in [Table 1.1](#) (Cohort 1), [Table 1.2](#) (Cohort 2), and [Table 1.3](#) (Cohorts 3 and 4).

Subjects must be resting quietly in a supine position or in the most recumbent position possible for at least 5 minutes before the ECG is obtained. The following ECG parameters will be recorded: HR, RR, PR, QRS, and QT and QT interval corrected for HR using Fridericia's formula (QTcF) intervals.

Electrocardiogram assessment will include interpretation of the tracings, eg, rhythm, presence of arrhythmia or conduction defects, morphology, any evidence of myocardial infarction, or ST segment, T-wave, and U-wave abnormalities. The investigator or designee is responsible for reviewing and over-reading the ECG interpretation, for assessing whether the ECG machine interpretation findings are accurate, appropriate, normal or abnormal, and for providing corrected interpretations as appropriate. In addition, any abnormal ECGs will be assessed for clinical significance.

Additional ECGs may be obtained if clinically indicated. Any additional relevant data obtained by the investigator during the course of this study will be supplied to the sponsor.

For any ECG that the investigator considers clinically significant, the investigator will:

- Repeat the ECG.
- Follow-up ECG(s) will be obtained if any significant abnormalities are detected after dose administration to document resolution and as clinically indicated.

Record as an AE any ECG that (1) is confirmed and the investigator considers clinically significant, (2) requires a subject to be discontinued from the study, (3) requires a subject to receive treatment, or (4) requires a change or discontinuation of the study drug (if applicable).

6.2.7 Other Safety Assessments

The Investigator or designee will collect a complete medical history at screening. Any updates to medical history will be recorded on Day -1.

Demographic characteristics including sex, age, race, and ethnicity will be recorded.

Height (cm) and weight (kg) without shoes will be recorded.

6.2.8 Protocol Deviation Reporting

Prospective approval of protocol deviations to recruitment and enrollment criteria, also known as protocol waivers or exemptions, are not permitted.

Deviations from the protocol with regard to subject enrollment or study conduct will also be noted in the source documentation.

7 CHANGES IN THE CONDUCT OF THE STUDY OR PLANNED ANALYSIS

Nadler's formula in the protocol was corrected to estimate PV rather than blood volume.

Except for Nadler's formula, the conduct of the study and planned analyses are consistent with the final study protocol (Version 1.0, dated 18 May 2017).

8 QUALITY CONTROL AND QUALITY ASSURANCE METHODS FOR DATA ANALYSIS

FAST BioMedical/ICON will implement and maintain quality control and quality assurance procedures with written standard operating procedures to ensure the study is conducted and data are generated, documented, and reported in compliance with the protocol, GCP, and applicable regulatory requirements.

9 PHARMACOKINETIC AND PHARMACODYNAMIC ASSESSMENTS

9.1 Pharmacokinetic Assessments

9.1.1 Pharmacokinetic Analysis

Pharmacokinetic parameters will be calculated from the plasma and urine concentration data using noncompartmental methods (Phoenix WinNonlin®, Version 6.3 or later, Pharsight Corporation, St. Louis, MO) and actual sampling times. The following PK parameters will be determined:

C_{\max}	Maximum observed plasma concentration
t_{\max}	The time that C_{\max} was observed
AUC_{0-12}	Area under the plasma concentration-time curve from time 0 to 12 hours; calculated using the linear/log trapezoidal rule (FD001 only)
AUC_{last}	Area under the plasma concentration-time curve from time 0 to the time of the last quantifiable concentration; calculated using the linear/log trapezoidal rule
AUC_{inf}	Area under the plasma concentration-time curve from time 0 extrapolated to infinity; calculated as $AUC_{\text{last}} + C_{\text{last}}/\lambda_z$, where C_{last} is the last measurable concentration
AUC_{extrap}	Area under the plasma concentration-time curve from the time of last observed concentration extrapolated to infinity expressed as a percent
$t_{1/2}$	Terminal elimination half-life; calculated as $\ln(2)/\lambda_z$
λ_z	Terminal elimination rate constant
CL	Total body clearance; calculated as Dose/ AUC_{inf}
CL_{r0-2}	Renal clearance from time 0 to 2 hours; calculated as Ae_{0-2}/AUC_{0-2} , where Ae_{0-2} is the amount of FD001 excreted in the urine from time 0 to 2 hours (FD001 only)
CL_{r2-12}	Renal clearance from time 2 to 12 hours; calculated as Ae_{2-12}/AUC_{2-12} , where Ae_{2-12} is the amount of FD001 excreted in the urine from time 2 to 12 hours (FD001 only)

CL _{r0-12}	Renal clearance from time 0 to 12 hours; calculated as Ae ₀₋₁₂ /AUC ₀₋₁₂ , where Ae ₀₋₁₂ is the amount of FD001 excreted in the urine from time 0 to 12 hours (FD001 only)
V _z	Volume of distribution during the terminal phase; calculated as CL/λ _z
V _{ss}	Volume of distribution at steady state; calculated as MRT _{inf} × CL, where MRT _{inf} is the mean residence time extrapolated to infinity
Ae ₀₋₂	Amount of FD001 excreted unchanged in the urine from time 0 to 2 hours
Ae ₂₋₁₂	Amount of FD001 excreted unchanged in the urine from time 2 to 12 hours
Ae ₀₋₁₂	Amount of FD001 excreted unchanged in urine from time 0 to 12 hours

Extrapolation methods will be used in Cohort 2, as needed, to correct concentration data after a second dose of FAST VFI in order to calculate PK parameters. Alternative methods (ie, compartmental modeling) may be used if extrapolation methods are inadequate. Computational details will be provided in a separate modeling and simulation analysis plan (MSAP).

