Ae 0-12	Amount of FD001 excreted unchanged in urine from time 0 to 12 hours

CONFIDENTIAL

Extrapolation methods will be used in Cohort 2, as needed, to correct concentration data after a second dose of FAST VFI in order to calculate PK parameters. Alternative methods (ie, compartmental modeling) may be used if extrapolation methods are inadequate. Computational details will be provided in a separate statistical analysis plan (SAP).

For the calculation of the FAST mGFR and PV in Cohort 2, residual levels of FD003 will be measured in the predose sample and those values subtracted from post-second-administration sample values to allow for a clean calculation of PV from dose 2. As these are healthy subjects we are not anticipating any level of residual FD001 that would affect the calculation of GFR.

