5 STUDY OBJECTIVES AND ENDPOINTS

5.1 Primary Objective

- To assess the safety and tolerability of VFI (employing the FAST plasma volume [PV] and measured glomerular filtration rate [mGFR] Technology) compared to Iohexol (employing Iohexol clearance methods) in healthy subjects and patients with impaired renal function
- To evaluate the PK of 5 kD carboxymethyl dextran (FD001) and 150 kD carboxymethyl dextran (FD003) in healthy subjects and patients with impaired renal function
- To evaluate the PK of FD001 and FD003 in healthy subjects receiving 2 doses of visible fluorescent injectate (VFI) separated by 24 hours to evaluate the reproducibility of the FAST mGFR Technology

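### Does the SAP need to fix which samples give the FD003 terminal slope in Cohort 2, or replace per-dose clearance by total dose over total AUC?

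*SAP*

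**What the plan says.** SAP 9.1.1 defines AUCinf as AUClast plus the last measurable concentration over lambda-z. It gives CL as "Total body clearance; calculated as Dose" over AUCinf, and lambda-z as the terminal elimination rate constant. No sample-selection rule for lambda-z is given, and no limit on the extrapolated percentage, although that percentage is among the listed parameters.

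For the repeat-dose cohort the same section adds three sentences. The first is "Extrapolation methods will be used in Cohort 2, as needed, to correct concentration data after a second dose of FAST VFI". The second is "Alternative methods (ie, compartmental modeling) may be used if extrapolation methods are inadequate". The third passes the detail on: "Computational details will be provided in a separate modeling and simulation analysis plan (MSAP"). Protocol 8.4.2 has the same first two sentences but a different destination: "Computational details will be provided in a separate statistical analysis plan (SAP").

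SAP 5.1 lists as a primary objective "To evaluate the PK of FD001 and FD003 in healthy subjects receiving 2 doses of visible fluorescent injectate (VFI) separated by 24 hours", with the stated purpose of judging how reproducible the mGFR measurement is. SAP Table 1.5 schedules Cohort 2 plasma samples from 15 minutes to 12 h after each dose, a sample just before dose 2, and samples at 24, 72, 168, 336 and 480 h after dose 2. SAP 10.1.9 summarises PK parameters by cohort and analyte, and elsewhere by treatment. It does not say by dose.

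**The concern.** Dose 2 arrives after roughly a quarter of an FD003 half-life, so only a small part of the dose-1 profile is ever seen alone. A dose-1 AUCinf would be mostly tail, and the tail is the last concentration divided by an estimated slope. If an analyst took that slope from the first 24 h, one subject's clearance could be wrong by half or more, and subtracting the dose-1 residual from the dose-2 data would inherit the same error.

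FD003 AUCinf, CL, Vz and Vss are primary endpoints. Cohort 2 supplies the only healthy values in this study, because SAP 10.1.9 limits Cohort 1 to renal clearance, amount excreted, Cmax and tmax. These values will be read beside Cohorts 3 and 4, which have one dose and samples to 480 h. The rule is also hard to trace: the protocol sends it to the SAP, and the SAP sends it to a further plan that is not among the documents. Neither says what makes extrapolation inadequate.

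FD001, mGFR and plasma volume are outside the concern. Protocol 8.4.2 gives plasma volume its own predose subtraction.

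**Working it through.** **Inputs from the documents.** FD003 half-life: 90 h in healthy subjects and 125 h in severe impairment (Protocol 3.4.3); 47-111 h in the first-in-human study (Protocol 3.4.2). Dose interval 24 h and sampling times: SAP Table 1.5. FD003 dose: 12 mg each time. Decline: mono-exponential (Protocol 3.4.3).

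**Assumptions.** Assay error 5% per sample, with 3% and 10% also shown; plasma volume 3 L; between-subject CV of clearance 15-30%. The documents give none of these. They also state no extrapolated share or precision, so there is no figure of the plan's to reproduce.

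**Step 1: extrapolated share.**

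- Dose 1 alone, 2^(-24/t½): 2^(-24/90) = 83.1%; 70.2% at 47 h; 86.1% at 111 h.
- Single dose to 480 h, 2^(-480/t½): 2.5% at 90 h; 7.0% at 125 h.
- Both doses of Cohort 2 as one profile, (1 + r)/2 × 2^(-480/t½) with r = 2^(-24/t½): (1 + 0.831)/2 × 0.0248 = 2.3% at 90 h; 0.1% at 47 h; 4.6% at 111 h.

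**Step 2: why the choice of slope matters.** The true slope is ln 2/90 = 0.00770 per h. The standard error of a log-linear slope is the assay error divided by the square root of the sum of squared time deviations.

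- Samples from 2 to 24 h (2, 2.83, 5.17, 6.17, 8, 12, 24 h): sum of squares 343.6, so 0.05/18.54 = 0.00270, or 35% of the slope. They span 22/90 = 0.24 half-lives, over which the concentration falls by only 16%.
- Samples on Days 5-22 (72, 168, 336, 480 h): sum of squares 97,920, so 0.05/312.9 = 0.00016, or 2.1% of the slope. They span 408/90 = 4.5 half-lives.

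Under linear mono-exponential decline, both doses decay at the same rate after dose 2. The late slope therefore also serves for the dose-1 tail.

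**Step 3: effect on clearance.** Simulated on the Table 1.5 times (20,000 subjects per setting, one compartment, linear/log trapezoid, half-life 90 h). Entries are the 5-95% range of estimated over true CL.

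| Method | 3% error | 5% error | 10% error |
|---|---|---|---|
| 2-24 h slope, dose 1 | 0.67-1.32 | 0.45-1.52 | 0.20-2.06 |
| Day 5-22 slope, dose 1 | 0.95-1.05 | 0.93-1.08 | 0.86-1.17 |
| Day 5-22 slope, corrected dose 2 | 0.94-1.07 | 0.90-1.12 | 0.83-1.28 |
| Total dose over total AUC | 0.98-1.02 | 0.97-1.03 | 0.93-1.07 |

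Residual subtraction with the 2-24 h slope breaks down (slope or a corrected concentration at or below zero) in 28% of subjects at 5% error. With the late slope it does so in none. A separate simulation at 47, 90 and 111 h and at 3-10% error, covering dose 1 and the pooled method, put the slopes in the same order.

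**Step 4: effect on the reported cohort mean.** The standard error relative to pooling is sqrt(b² + w²)/sqrt(b² + 0.020²). Here b is the between-subject CV, and w is the SD of log CL at 5% error: 0.42, 0.047 and 0.066 for the first three rows, and 0.020 for pooling.

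- 2-24 h slope: 0.446/0.151 = 2.9 at b = 0.15; 0.516/0.301 = 1.7 at b = 0.30.
- Day 5-22 slope, dose 1: 1.04 and 1.01.
- Day 5-22 slope, corrected dose 2: 1.08 and 1.02.

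Nearly all the loss comes from using the early slope. Once the late slope is used, pooling has little left to recover.

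**The case for a change.** The strongest case for a change is that it costs little. Every sample is already scheduled, and one sentence naming the Day 5-22 samples, with a definition of inadequate, would rule out a choice of slope after the data are seen. The early slope is also biased if distribution is slow. With an added 6 h distribution phase carrying 15% of the initial concentration, the 2-24 h slope gives a median clearance of 1.49 times the truth. Protocol 3.4.3 does report delayed dispersion of FD003. Pooling would go further. It uses doses that are "weighed and documented before and after dosing in order to calculate the exact amount of product administered" (SAP 6.1.6), and it leaves only about 2.3% of the AUC to extrapolation.

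What stands is narrow. The protocol and SAP do not contain the rule, so it cannot be confirmed from them as prespecified. The plan they defer to may contain it. Naming the samples in that plan, and printing the extrapolated percentage beside any per-dose AUCinf or CL, would be tidy.

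The rest does not carry. The large error belongs to a slope that the SAP never commits to. Pooling redefines CL, Vz and Vss, which are primary endpoints, and would need an entry in SAP Section 7, which now says "Except for Nadler's formula, the conduct of the study and planned analyses are consistent with the final study protocol". It assumes clearance unchanged between doses, so it cannot compare them, in the one cohort designed for repeat dosing. Even the 83% applies only if AUCinf is reported per dose, which the SAP does not say.

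**Conclusion.** The arithmetic is sound but does not call for a change. This is a detail left to a named technical plan, and a pharmacokineticist would fill it sensibly. The SAP asks for a terminal rate constant, the marker's half-life is about 90 h, and four samples lie between 72 and 480 h after dose 2. Taking the terminal slope from the first 24 h would ignore all of them. If extrapolation still proved inadequate, SAP 9.1.1 already permits compartmental modelling.

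With the natural late slope, per-subject clearance is within about 8% of truth for dose 1 and 12% for corrected dose 2 (5-95% range, 90 h, 5% assay error). The standard error of the cohort mean is 1-8% above that of pooling. In a descriptive study with up to 8 subjects per cohort and no formal hypotheses, that difference would not alter how the results are read. Pooling is a reasonable sensitivity estimate but no better as the primary definition.

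The sizes rest on the assumed assay error, mono-exponential decline, and a between-subject CV of 15-30%. At 10% assay error the late-slope ranges widen to 0.86-1.17 (dose 1) and 0.83-1.28 (dose 2). The ordering of the methods holds at every error level and half-life tried. The different destinations given in the protocol and the SAP are a matter of document housekeeping and change no analysis.
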